4.0 Study Design and Randomization

4.1 Study Design and Randomization (P1, EHR-based antibiotic decision support)

Effectiveness of the EHR-based antibiotic decision support application for promoting guideline-concordant antibiotic prescribing in children presenting for emergency care will be evaluated in a pragmatic, cluster randomized crossover study conducted over a period of 18 months that includes two respiratory seasons. Our institutions possess demonstrated experience in the execution of these pragmatic designs.¹⁷⁻²¹ Crossover will occur each month in a randomly determined sequence within each hospital. To ensure balanced representation of each arm in periods of both low and high pneumonia prevalence, randomization will occur in 3 permuted blocks (size=6). The cluster-randomized crossover design also improves efficiency and reduces potential problems related to cluster imbalance when using a small number of clusters.⁶⁷ The antibiotic decision support application will be provided to those randomized to the intervention arm, whereas the control arm will receive usual care. Due to the nature of the intervention, blinding of treating providers will not be possible. Importantly, since this is a trial focused on provider behavior, all children will receive standard of care management. All treatment decisions will be made by the clinical providers and will not be restricted or altered in any way.

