8.0 Statistical Considerations

8.1 Power and Sample Size (P1)

Based on ED and hospitalization data from our hospitals during the conduct of the EPIC study, we anticipate nearly 2000 total children with pneumonia will be evaluated annually during the conduct of these studies. Assuming conservatively that data for 750 children are enrolled in each arm, and 30% guideline-concordant antibiotic use in the usual care arm (based on our prior study of antibiotic use in the EPIC cohort)²³, we will be able to detect an absolute difference of $\geq 6.8\%$ in guideline-concordant prescribing at an alpha level of 0.05 with 80% power. Effective sample size may be reduced due to the cluster randomized nature of the study (a conservative estimate for effective sample size would be around 500 children in each arm).

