8.2 Analysis (P1)

Analyzing data from cluster randomized crossover trials requires accounting for correlations within clusters and time periods. As outlined by Turner et al.,²¹ we will use a hierarchical and mixed effects logistic regression model, a complex analytic approach which offers flexibility regarding model assumptions and incorporation of cluster-level and individual-level covariates. We will also use a weighted, cluster-level logistic regression to compare guideline-concordant antibiotic prescribing between groups. In this analysis, data for each cluster are collapsed into a single summary measure, and the summary measures are then analyzed as if they were raw data, facilitating simple data reporting and interpretation.²¹ Both methods perform well and are used frequently in the analysis for traditional cluster randomized trials without crossover. Important baseline covariates (e.g., age, sex, race, site of care, frequency of bacteremia and other pneumonia-related complications) will also be assessed and included as model covariates. Similar analyses will be conducted for the proposed secondary and exploratory outcomes using hierarchical and mixed effects logistic regression models for binary outcomes and frailty models for time to first antibiotic.

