## **6.2 Sample Size and Power**

### **6.2.1 Phase 1**

Based on ED and hospitalization data from our hospitals during the conduct of the EPIC study, we anticipate nearly 2000 total children with pneumonia will be evaluated annually during the conduct of these studies. Assuming conservatively that data for 750 children are enrolled in each arm, and 30% guideline-concordant antibiotic use in the usual care arm (based on our prior study of antibiotic use in the EPIC cohort), we will be able to detect an absolute difference of  $\geq 6.8\%$  in guideline-concordant prescribing at an alpha level of 0.05 with 80% power. Effective sample size may be reduced due to the cluster randomized nature of the study (a conservative estimate for effective sample size would be around 500 children in each arm).

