## **6.3 Randomization**

### **6.3.1 Phase 1**

During the 18-month study period, EHR-based antibiotic decision support will be active monthly (4-week blocks) based on the cluster randomized scheme at each hospital. To ensure balanced representation of each arm in periods of both low and high pneumonia prevalence, randomization will occur in 3 permuted blocks (size=6). The antibiotic decision support application will be provided to those randomized to the intervention arm, whereas the control arm will receive usual care. Participants enrolled during the month with antibiotic decision support will be assigned to the intervention arm, and participants receiving usual care will be in the control arm. Participants will be blinded to the treatment assignments and study staff and providers will not be blinded to treatment arm assignments due to the nature of the interventions.

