### **10.1 Primary Objective**

The primary objective (PO 1) of the study is to compare proportions of participants exclusively receiving guideline-concordant 1st line antibiotic therapy during the first 24 hours of care with or without EHR-based decision support in children 0.6-17 years of age presenting for emergency care. The hypothesis for this primary objective is that the proportion of participants exclusively receiving guideline-concordant 1st line antibiotic therapy during the first 24 hours of care is higher in the group receiving EHR-based decision support vs. the group receiving usual care. This information is captured through chart review and entered in the REDCap database. The antibiotics received by a participant is concordant yes (1) or no (0) based on Appendix 1 table, for this analysis.

The proportions will be compared between the intervention arm versus the control arm using a Cochran-Mantel-Haenszel method in a stratified analysis by site to control for two sites at the alpha 0.05 level. The proportion difference and corresponding 95% confidence interval for concordance of antibiotics with or without adjusting for sites will also be calculated.

We will use a hierarchical and mixed effects logistic regression model, a complex analytic approach which offers flexibility regarding model assumptions and incorporation of cluster-level and individual-level covariates. The outcome is proportions of participants exclusively receiving guideline-concordant 1st line antibiotic therapy during the first 24 hours of care and the main exposure variable is intervention vs. usual care. The month of each participant enrolled will be treated as a random effect. We will also use a weighted, cluster-level logistic regression to compare guideline-concordant antibiotic prescribing between groups. In this analysis, data for each cluster are collapsed into a single summary measure, and the summary measures are then analyzed as if they were raw data, facilitating simple data reporting and interpretation. Important baseline covariates (e.g., age, sex, race, site, season, frequency of bacteremia and other pneumonia-related complications) will also be assessed and included as model covariates.

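### Phase 1's 6.8-point detectable difference assumes 750 independent children per arm; at the plan's own conservative effective size of about 500 it is about 8.4 points, a figure neither document gives

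*Protocol*

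**What the plan says.** Protocol 8.1 and SAP 6.2.1 carry the same Phase 1 power paragraph. It starts from expected volume ("we anticipate nearly 2000 total children with pneumonia will be evaluated annually") and then fixes the planning size: "Assuming conservatively that data for 750 children are enrolled in each arm". With 30% concordance under usual care, alpha 0.05 and 80% power, it gives a detectable absolute difference of at least 6.8 percentage points.

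The paragraph closes with a caution, "Effective sample size may be reduced due to the cluster randomized nature of the study", and a number for it: "a conservative estimate for effective sample size would be around 500 children in each arm". No detectable difference, power, intracluster correlation or design effect is given for that smaller size.

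On design, Protocol 4.1 says "Crossover will occur each month in a randomly determined sequence within each hospital", and SAP 6.3.1 says "During the 18-month study period, EHR-based antibiotic decision support will be active monthly". Assignment is therefore by hospital and month, not by child. On analysis, Protocol 8.2 says "Analyzing data from cluster randomized crossover trials requires accounting for correlations within clusters and time periods", and the mixed model in SAP 10.1 reflects this: "The month of each participant enrolled will be treated as a random effect".

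**The concern.** The only detectable difference stated for Phase 1 comes from a formula for independent children, while the design, the analysis section and the paragraph's own last sentence all say the children are not independent. The plan supplies the allowance for clustering but not its consequence.

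At stake is how the trial is read. A monitoring board, an ethics committee or a later reader uses this paragraph to learn what Phase 1 could detect. If the trial found no significant difference, an unqualified 6.8 points would overstate the range of effects it was able to detect under the plan's own conservative scenario.

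**Working it through.** **Inputs.** From Protocol 8.1 and SAP 6.2.1: usual-care rate p1 = 0.30; alpha 0.05; power 80%; n = 750 enrolled per arm; effective n of about 500 per arm. The documents do not say whether the test is one- or two-sided; step 1 settles this by reproduction.

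**Formula.** Two-proportion normal approximation, equal arms, pooled variance under the null, p̄ = (p1 + p2)/2:

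power = Φ{ [ |p2 − p1|·√n − z·√(2p̄(1 − p̄)) ] / √( p1(1 − p1) + p2(1 − p2) ) }, with z = 1.960 for two-sided 0.05.

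**Step 1: the plan's figure (n = 750, p2 = 0.368).**
- p̄ = 0.334; √(2 × 0.334 × 0.666) = 0.6670; √(0.2100 + 0.2326) = 0.6653.
- (0.068 × 27.386 − 1.960 × 0.6670)/0.6653 = (1.862 − 1.307)/0.6653 = 0.834.
- Power = Φ(0.834) = 79.8%.
- Solving for exactly 80% gives 6.82 points. The sample size for 6.8 points is 754 per arm.

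So the stated 6.8 reproduces. Other two-sided formulas agree (unpooled 6.81, arcsine 6.82; 6.96 with continuity correction). A one-sided test at 0.05 would give 6.03, so the stated figure implies a two-sided test. No design effect enters.

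**Step 2: the same difference at the plan's effective size (n = 500, p2 = 0.368).**
- (0.068 × 22.361 − 1.307)/0.6653 = (1.521 − 1.307)/0.6653 = 0.321.
- Power = Φ(0.321) = 62.6%.

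**Step 3: the difference detectable at n = 500 (p2 = 0.384).**
- p̄ = 0.342; √(2 × 0.342 × 0.658) = 0.6709; √(0.2100 + 0.2365) = 0.6682.
- (0.084 × 22.361 − 1.960 × 0.6709)/0.6682 = (1.878 − 1.315)/0.6682 = 0.843.
- Power = Φ(0.843) = 80.0%.

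The detectable difference is therefore 8.40 points (unpooled 8.37, arcsine 8.39, continuity-corrected 8.61). Against 6.82 this is 8.40/6.82 = 1.23, about 23% larger.

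**Step 4: a larger effect at n = 500 (p2 = 0.40).**
- (0.100 × 22.361 − 1.960 × 0.6745)/0.6708 = (2.236 − 1.322)/0.6708 = 1.36.
- Power is about 91%.

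| Per arm | Detectable at 80% power | Power for 6.8 points |
|---|---|---|
| 750 independent | 6.82 points | 79.8% |
| 500 effective | 8.40 points | 62.6% |

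**The case against.** **No number is wrong, and the reduction is disclosed.** This stands as far as it goes. The 6.8 is correct for its stated inputs, the very next sentence warns about clustering, and a statistician could derive 8.4 from the page. The defect is an unfinished power statement rather than a miscalculation. But 6.8 remains the only sensitivity figure offered, and most readers will not see from an effective size alone that power for it falls from 80% to about 63%.

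**No target difference is set.** This also stands. The 6.8 is an output of the calculation, so 63% is power against that output and not against a difference the plan says it must detect. A reader might infer that Phase 1 is underpowered. The documents do not support that.

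**Enrolment may exceed 750 per arm.** True: the plan calls 750 conservative. Nearly 2000 evaluated a year over 18 months is nearly 3,000, or 1,500 per arm, as an upper bound since not all will be eligible. (Protocol 13.0 gives 24 months for Phase 1 instead of 18, so this volume is itself unsettled.)

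A reader might infer that extra enrolment simply restores the 6.8 points. That is not established, because the number of hospital-months is fixed and each further child in the same month adds less information. How much less depends on a correlation the documents do not give. Two assumptions illustrate the range at the upper bound:
- If the 500/750 ratio held, 1,500 × 2/3 = 1,000 effective per arm, and 5.9 points detectable.
- If instead a constant correlation held over 2 × 18 = 36 equal hospital-months, 500/750 implies (1.5 − 1)/(41.7 − 1) = 0.0123. The design effect at 83.3 children per hospital-month is then 1 + 82.3 × 0.0123 = 2.01, leaving about 745 effective per arm and 6.8 points detectable.

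Even with every evaluated child enrolled, the second case only just returns to the stated figure. At realistic enrolment the offset could be partial.

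**500 may be too pessimistic, or not pessimistic enough.** With no correlation in the documents, neither can be shown. The point uses 500 because it is the plan's own figure.

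**Conclusion.** The point holds as a correction to the planning statement. The 6.8-point figure is valid for 750 independent children per arm and makes no allowance for randomisation by hospital and month. At 750 enrolled, under the plan's own conservative effective size, the stated 80% power for 6.8 points is not delivered: power is about 63%, and 80% is reached only at about 8.4 points.

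This rests on three things: a two-sided 0.05 test, inferred because only that reproduces 6.8; the reading that the effective 500 corresponds to 750 enrolled, which is the natural sense of the paragraph; and the approximate nature of 500 itself, so that 8.4 and 63% carry the word *about*.

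It is not a forecast of what Phase 1 will achieve. Nor does it show that the planned modelling ignores clustering, since the mixed model in SAP 10.1 includes month as a random effect.

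**What to change.** In Protocol 8.1 and SAP 6.2.1:

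1. State that the 6.8-point figure assumes 750 independent children per arm (and that the test is two-sided, if that is confirmed).
2. After the effective-size sentence, add: *At the conservative effective sample size of about 500 per arm, the trial has 80% power to detect an absolute difference of about 8.4 points (about 63% power for 6.8 points).*

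If the authors wish to mention higher enrolment, the wording should go no further than that it *could partly offset this*. An enrolment target to restore 6.8 points should not be given without a stated and justified correlation.

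The cost is one clause and one sentence in each of two sections. The downside is presentational: the detectable difference under clustering reads about 23% larger than the present headline figure. Enrolment, design and analysis do not change.

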8.2 Analysis (P1)

Analyzing data from cluster randomized crossover trials requires accounting for correlations within clusters and time periods. As outlined by Turner et al.,²¹ we will use a hierarchical and mixed effects logistic regression model, a complex analytic approach which offers flexibility regarding model assumptions and incorporation of cluster-level and individual-level covariates. We will also use a weighted, cluster-level logistic regression to compare guideline-concordant antibiotic prescribing between groups. In this analysis, data for each cluster are collapsed into a single summary measure, and the summary measures are then analyzed as if they were raw data, facilitating simple data reporting and interpretation.²¹ Both methods perform well and are used frequently in the analysis for traditional cluster randomized trials without crossover. Important baseline covariates (e.g., age, sex, race, site of care, frequency of bacteremia and other pneumonia-related complications) will also be assessed and included as model covariates. Similar analyses will be conducted for the proposed secondary and exploratory outcomes using hierarchical and mixed effects logistic regression models for binary outcomes and frailty models for time to first antibiotic.

An important consideration in our analysis is the possibility of contamination effects in the usual care arm related to changes in provider behavior due to past exposures and awareness of the intervention. Such contamination would be expected to bias toward the null hypothesis. We posit that such effects will be of minor concern since 1) guideline-concordant prescribing at our institutions remains low despite the presence of both national and local practice guidelines and order sets for several years; 2) the ED is a busy environment with many providers (e.g., 40+ ED faculty plus mid-level providers and fellows/residents at Vanderbilt alone), such that repeated exposure to the intervention by any one provider would be infrequent, particularly early during the study period and during times of low pneumonia prevalence; and 3) resident physicians, the providers responsible for the majority of order entry and thus directly exposed to the intervention, rotate on a monthly schedule and only work in the ED once each year. We have designed our randomization and monthly crossover periods around these important considerations. Nevertheless, we acknowledge the potential for contamination, and we will formally evaluate for such effects in a secondary analysis by modeling the monthly proportions of guideline-concordant prescribing in each arm over the duration of the study period. We will then compare prescribing trends in both arms with a historical trend estimated from monthly proportions of guideline-concordant prescribing in the year prior to study initiation. By comparing prescribing trends in each arm to this historical trend, we will estimate both the degree of potential contamination as well as the independent impact of the intervention.

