8.5 Analysis (P2)

Logistic regression models will be performed to compare appropriate site of care disposition between the two study arms, controlling for important baseline covariates (e.g., age, season, provider type) to maximize power. Robust standard errors will be calculated to account for hospital clustering effects. We will also perform analyses to assess for interactions between two study arms and predicted risk for severe outcomes, age, provider type, and initial site of care, to identify subgroups in whom decision support may be most useful. Similar analyses will be conducted for the proposed secondary and exploratory outcomes along with cox regression model for hospital length of stay outcome.

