### **11.1 Primary Objective**

The primary objective (PO 1) of the study is to compare proportions of appropriate overall site of care disposition with or without EHR-based prognostic decision support in children 0.6-17 years of age presenting for emergency care. The hypothesis for this primary objective is that the proportion of appropriate site of care disposition is higher in the group receiving EHR-based prognostic decision support vs. the group receiving usual care. This information is captured through chart review and entered in the REDCap database. An investigator in both Nashville and Pittsburgh will be in charge of outcome assessment review, blinded to intervention assignment, and will decide whether site of care disposition is appropriate, yes (1) or no (0), based on Appendix 2 table for this analysis.

The proportions will be compared between the intervention arm versus the control arm using a Cochran-Mantel-Haenszel method in a stratified analysis by site to control for two sites at the alpha 0.05 level. The proportion difference and corresponding 95% confidence interval for concordance of antibiotics with or without adjusting for sites will also be calculated.

We will conduct a multivariable logistic regression model to compare appropriate site of care disposition between the two study arms, controlling for important baseline covariates. Important baseline covariates (e.g., age, sex, race, site, season, month, frequency of bacteremia and other pneumonia-related complications) will also be assessed and included as model covariates. Robust standard errors will be calculated to account for hospital clustering effects. We will also perform analyses to assess for interactions between two study arms and predicted risk for severe outcomes, age, provider type, and initial site of care, to identify subgroups in whom decision support may be most useful.

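### Covariates called baseline (bacteremia, complications and, in the protocol, site of care) can arise after allocation, so the adjusted estimates can be biased in either direction

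*Protocol*

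**What the plan says.** Protocol 8.2 describes the Phase 1 regression models and says that important baseline covariates will be assessed and included. Besides age, sex and race, its examples are "site of care, frequency of bacteremia and other pneumonia-related complications".

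SAP 10.1 gives the Phase 1 list as "age, sex, race, site, season, frequency of bacteremia and other pneumonia-related complications". Here the entry is site, which SAP 7.2 uses for the two hospitals, and not site of care. SAP 11.1 reuses the list for Phase 2, ending in "season, month, frequency of bacteremia and other pneumonia-related complications". For the same Phase 2 model, Protocol 8.5 speaks of "controlling for important baseline covariates (e.g., age, season, provider type) to maximize power".

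The remaining models in SAP 10.2, 10.3, 11.2 and 11.3 take similar covariates. They cover revisits, hospitalizations, death, delayed ICU transfer and length of stay. The baseline data listed in SAP 9.1 carry no time cut-off either.

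The test that the SAP ties to alpha 0.05 is, in each phase, a CMH comparison stratified by hospital. The covariates enter only the regressions.

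**The concern.** In a randomised comparison, adjustment is safe for variables fixed before allocation. If a variable can respond to allocation, conditioning on it removes the part of the effect that runs through it. It can also create an association between arm and unmeasured severity. The adjusted estimate then no longer describes the total effect of giving providers the tool.

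Bacteremia is known only once a culture grows, complications can develop during the stay, and site of care is decided in the ED after the arm is set. Some of these variables also help to define the outcome. The safety comparisons are exposed too: adjusting death or delayed ICU transfer for complications conditions on events close to the outcome itself.

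**Working it through.** **1. Timing and overlap with the outcome**

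- *Phase 1 allocation* is fixed by calendar month: "Participants enrolled during the month with antibiotic decision support will be assigned to the intervention arm" (SAP 6.3.1). Disposition, culture results and later complications can all follow it.
- *Phase 1 outcome.* Protocol Table 1 uses disposition and complicated disease to decide which regimens count as concordant. Site of care and complications are therefore inputs to the outcome.
- *Phase 2 allocation* occurs when the provider confirms pneumonia (SAP 6.3.2), and the tool is intended to change disposition. Under SAP Appendix 2, ICU transfer within 24 h makes a ward disposition inappropriate, so a complication that prompts transfer is tied to outcome failure.

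**2. The plan's own figures**

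These use a two-sided two-proportion test with pooled variance under the null.

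- Phase 1 (750 per arm, 30% control): detectable difference 6.82 points; power at 36.8% is 79.8%. The stated 6.8% reproduces.
- Phase 2 (1,000 per arm, 90% control): detectable difference 3.45 points; power at 93.4% is 78.7%. The stated 3.4% reproduces to rounding.

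Both calculations are unadjusted, so changing the covariate list does not alter them.

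**3. Phase 1 illustration on the risk-difference scale**

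These assumptions are not in the documents. A binary post-allocation covariate M has 50% prevalence under usual care and a log odds ratio of +1 with concordance. The direct effect is set to give +6.8 points when the arm does not shift M. A logistic model with arm and M is fitted in the population limit and standardised.

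| Shift in M by arm | Total effect | Adjusted effect | Direction |
|---|---|---|---|
| +10 points | 9.07 | 6.92 | toward null |
| +5 | 7.93 | 6.86 | toward null |
| 0 | 6.80 | 6.80 | none |
| -5 | 5.67 | 6.74 | away from null |
| -10 | 4.53 | 6.68 | away from null |

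Adding an unmeasured severity factor, and also trying a log odds ratio of -1, gives gaps of about 0.7 to 1.4 points for a 5-point shift and 1.3 to 2.8 points for a 10-point shift, in both directions. A rare covariate (5%, odds ratio 0.3) shifted by -2 or +2 points gives 7.25 against 6.83, or 6.35 against 6.77.

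**4. Phase 2 illustration on the odds-ratio scale**

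From the plan: 90% against 93.4% appropriate and 1,000 per arm. Assumed: the 10% control failures are 5% under-triage and 5% over-triage, and complications are recorded in q = 30%, 50% or 80% of under-triaged children against 5% of all others.

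Unadjusted OR = (0.934/0.066)/(0.90/0.10) = 14.15/9 = 1.57.

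Among appropriate dispositions M is 5% in both arms. Within stratum m, therefore:

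OR(m) = 1.572 × P(m | failure, control) / P(m | failure, intervention).

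With q = 80%, P(M | failure, control) = 0.5×0.80 + 0.5×0.05 = 0.425.

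- *Under-triage only (5% to 1.6%).* The under-triaged share of failures is 1.6/6.6 = 0.242, so P(M | failure, intervention) = 0.232. OR is 1.572×0.425/0.232 = 2.88 with M and 1.572×0.575/0.768 = 1.18 without.
- *Over-triage only (5% to 1.6%).* The share is 5/6.6 = 0.758 and the probability is 0.618. OR is 1.08 with M and 2.37 without.
- *Both equally (5% to 3.3% each).* The share stays at 0.5, so OR is 1.57 in both strata.

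The main-effects logistic model combines the strata as follows:

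| Tool acts on | q = 30% | 50% | 80% | Change in log OR | Wald power (unadjusted 78%) |
|---|---|---|---|---|---|
| Under-triage only | 1.56 | 1.53 | 1.46 | -2% to -16% | 76% to 59% |
| Over-triage only | 1.59 | 1.64 | 1.76 | +3% to +25% | 79% to 86% |
| Both equally | 1.57 | 1.57 | 1.57 | none | 77% to 72% |

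**5. Scale matters**

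Part of an odds-ratio change comes from moving from a marginal to a conditional odds ratio. With q = 80% and over-triage only, M is recorded in 8.75% of both arms. The stratum risk differences are 0.0194 (with M) and 0.0354 (without), so the standardised difference is 0.0875×0.0194 + 0.9125×0.0354 = 0.034, which is unchanged. Under-triage only gives 0.07475×0.2389 + 0.92525×0.0090 = 0.026. Acting equally gives 0.0811×0.1105 + 0.9189×0.0220 = 0.029. The Phase 2 shift away from the null is thus specific to the odds ratio, which is what the logistic model reports. In Phase 1, both directions occur on the risk-difference scale.

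**The case against.** Four points on the other side have force.

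- **The formal test is untouched.** This is correct: bacteremia and complications do not enter the CMH comparison or its risk difference in either phase. But CMH stratifies by hospital only, and Protocol 8.2 says the crossover design requires correlation within clusters and periods to be handled. The mixed model is the individual-level Phase 1 analysis that does so by month, and it takes these covariates. The cluster-level model is affected too if it is adjusted.
- **Site of care is not in the SAP.** Also correct. The later document may have dropped it deliberately, but neither document says so and the two lists conflict.
- **Some of these conditions are truly baseline.** An empyema present at triage is a patient characteristic even if confirmed later, and the Phase 1 tool takes disposition as an input to its advice. If the arm does not shift the covariate, the standardised risk difference is unbiased. This supports a time limit on the variables rather than a blanket ban. It does not support lists with no limit at all.
- **The lists are only examples.** They are, so the absence of provider type from the SAP 11.1 list is weak evidence by itself; the SAP still tests its interaction with arm. Open lists do, however, leave the final covariate set to be chosen later.

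A reader might infer that the bias runs toward the null and so is conservative. The documents do not support this. The rationale in Protocol 2.0 cites both likely unnecessary short stays and delayed ICU care, so neither mechanism can be assumed.

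**Conclusion.** The concern stands for the covariate-adjusted regressions. The plan labels as baseline, and includes in the models, variables that can arise or be detected after allocation and that are partly tied to the outcomes. The estimates can be biased in either direction. The documents give neither the direction nor the size, because they contain no complication rates by arm or by triage error.

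Under the stated assumptions, the Phase 2 odds ratio of 1.57 could be reported as anything from 1.46 to 1.76. A 5- to 10-point shift in a common Phase 1 covariate moves the adjusted difference by about 0.7 to 2.8 points, against a design difference of 6.8.

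Three stronger readings should be resisted. The alpha-0.05 CMH tests are not compromised. The power figures in the Phase 2 table concern the adjusted model only and are not a loss of trial power. Nothing in the documents shows that either tool does change bacteremia or complication rates. The point is worth correcting before analysis, but it does not threaten the primary test.

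**What to change.** - Delete site of care from the covariates in Protocol 8.2.
- In Protocol 8.2, SAP 10.1 and SAP 11.1, remove bacteremia and complications from the main adjusted models unless each is defined as present and known at or before allocation or ED triage. Apply the same rule to the models in SAP 10.2, 10.3, 11.2 and 11.3.
- Report variables that arise later descriptively or in a labelled sensitivity analysis.
- Align Protocol 8.2 with SAP 10.1, and Protocol 8.5 with SAP 11.1, as closed lists. If provider type is kept, confirm that it is collected: the data lists in Protocol 7.3 and SAP 7.1 do not name it.
- Optionally, for Phase 2, use the tool's predicted risk at enrolment, computed in both arms, as the baseline severity covariate.

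The cost is wording changes and possibly slightly less precision in the adjusted models. Sample size and the CMH tests do not change.
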